#### 3.0 PATIENT ELIGIBILITY

Subjects must meet all of the eligibility criteria to be enrolled to the study. Study treatment may not begin until a subject is enrolled.

# 3.1 Eligibility Criteria

Patients must have a pathologically confirmed adenocarcinoma of the biliary tract (intra-hepatic, extra-hepatic (hilar, distal) or gall bladder) that is not eligible for curative resection, transplantation, or ablative therapies. Tumors of mixed histology are excluded.

- 3.1.2 Patients must have received 1st line platinum-based systemic chemotherapy for advanced BTC for 4-6 months (16-24 weeks) without radiologic or clinical progression. Last systemic infusion of 1st line platinum-based therapy may not be more than 4 weeks from study informed consent. Prior peri-operative chemotherapy is permitted provided it was completed > 6 months from start of platinum-based therapy for advanced disease.
- 3.1.3 Prior surgical resection, radiation, chemoembolization, radioembolization or other local ablative therapies are permitted if completed ≥ 4 weeks prior to enrollment AND if patient has recovered to ≤ grade 1 toxicity.
- 3.1.4 Patients must have measurable disease (as per RECISTv1.1) in at least one site not previously treated with radiation or liver directed therapy (including bland, chemo- or radio-embolization, or ablation) either within the liver or in a metastatic site unless the patient has had complete response to 1st line platinum-based therapy.
- 3.1.5 Age≥18 years
- 3.1.6 Child-Pugh score of A or B7
- 3.1.7 ECOG performance status of 0-1
- 3.1.8 Ability to understand and willingness to sign IRB-approved informed consent
- 3.1.9 Available archived tissue (FFPE block or 20 unstained slides from prior core biopsy or surgery)
- 3.1.10 Must be able to tolerate CT and/or MRI with contrast
- 3.1.11 Adequate organ function obtained ≤ 2 weeks prior to registration

| absolute neutrophil count | ≥ 1500/mm                      |
|---------------------------|--------------------------------------------|
| hemoglobin                | ≥ 9 g/dL                                   |
| platelets                 | ≥ 100,000/mm                   |
| serum creatinine          | ≤ 1.5 x ULN                                |
|                           |                                            |
| albumin                   | ≥ 3.0 g/dL                                 |
| AST/ALT                   | ≤ 3.0 x ULN (≤5 x ULN if liver metastasis) |
| total bilirubin           | ≤ 1.5 x ULN                                |

- 3.1.12 Must not have a diagnosis of immunodeficiency, or received systemic steroid therapy, or any other form of immunosuppressive therapy within 14 days prior to trial treatment. Short bursts of steroids of 5-7 days (for COPD exacerbation or other similar indication) are allowed.
- 3.1.13 No prior history of solid organ transplantation or brain metastasis (unless treated and stable).
- 3.1.14 Must not have undergone a major surgical procedure < 4 weeks prior to registration.
- 3.1.15 Must not have an active second malignancy other than non-melanoma skin cancer or cervical carcinoma in situ. Patients with history of malignancy are

eligible provided primary treatment of that cancer was completed > 1 year prior to registration and the patient is free of clinical or radiologic evidence of recurrent or progressive malignancy.

- 3.1.16 Must have no ongoing active, uncontrolled infections (afebrile for > 48 hours off antibiotics)
- 3.1.17 Must not have received a live vaccine within 30 days of planned start of the study therapy.
- 3.1.18 Must not have a psychiatric illness, other significant medical illness, or social situation which, in the investigator's opinion, would limit compliance or ability to comply with study requirements.
- 3.1.19 Women must not be pregnant or breastfeeding since rucaparib and/or nivolumab may harm the fetus or child. All females of childbearing potential (not surgically sterilized and between menarche and 1-year post menopause) must have a blood or urine test to rule out pregnancy within 2 weeks prior to registration.
- 3.1.20 Women of child-bearing potential and men must agree to use 2 methods of adequate contraception (hormonal plus barrier or 2 barrier forms) OR abstinence prior to study entry, for the duration of study participation, and for 6 months (for women) and 7 months (for men) following completion of study therapy
- 3.1.21 Participants must not have an active, known or suspected autoimmune disease which may affect vital organ function, or has/may require systemic immunosuppressive therapy for management. Participants with type I diabetes mellitus, hypothyroidism only requiring hormone replacement, skin disorders (such as vitiligo, psoriasis, or alopecia) not requiring systemic treatment, or conditions not expected to recur in the absence of an external trigger are permitted to enroll.
- 3.1.22 Participants must not have a condition requiring systemic treatment with either corticosteroids (>10 mg daily prednisone equivalent) or other immunosuppressive medications within 14 days of start of study treatment. Inhaled or topical steroids, and adrenal replacement steroid doses >10 mg daily prednisone equivalent, are permitted in the absence of active autoimmune disease.
- 3.1.23 Patients may not have previously received anti PD1/PDL1 antibodies or PARP inhibitor for treatment of this cancer.

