#### 7.1.2 Disease Parameters

Measurable disease. Measurable lesions are defined as those that can be accurately measured in at least one dimension (longest diameter in the plane of measurement is to be recorded) with a minimum size of:

- 10 mm by CT scan (irrespective of scanner type) for studies with a slice thickness of <5mm or twice the slice thickness or MRI

- 10 mm caliper measurement by clinical exam (lesions which cannot be accurately measured with calipers should be recorded as nonmeasurable)
- 20 mm by chest X-ray (if clearly defined and surrounded by aerated lung)

All tumor measurements must be recorded in millimeters (or decimal fractions of centimeters).

Malignant lymph nodes: To be considered pathologically enlarged and measurable, a lymph node must be ≥15mm in short axis when assessed by CT scan (CT scan slice thickness recommended to be no greater than 5 mm). At baseline and in follow-up, only the short axis will be measured and followed.

Note: Tumor lesions that are situated in a previously irradiated area will only be considered measurable, if they have had subsequent progression by at least 5 mm

Non-measurable disease. All other lesions (or sites of disease), including small lesions (longest diameter <10 mm using CT scan), are considered non-measurable disease. Bone lesions without measurable soft tissue component, leptomeningeal disease, ascites, pleural/pericardial effusions, lymphangitis cutis/pulmonitis, inflammatory breast disease, abdominal masses (not followed by CT or MRI), and cystic lesions are all non-measurable.

Target lesions. All measurable lesions up to a maximum of 2 lesions per organ and 5 lesions in total should be identified as target lesions and recorded and measured at baseline. Target lesions should be selected on the basis of their size (non-nodal lesions with the longest diameter), be representative of all involved organ(s), but in addition should be those that lend themselves to reproducible repeated measurements. If a non-nodal lesion is either not present or is initially measured with longest diameter <10mm as a non-target then grows to ≥10mm after baseline, this lesion then becomes a new target lesion as per irRECIST criteria. The non-nodal longest diameter is then added to the sum of diameters, and patient response is calculated with the new lesion.

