#### 7.1.4 Response Criteria

# 7.1.4.1 Evaluation of Target Lesions

Prior to the first PD assessment, patients will be evaluated according the following RECISTv1.1 response:

Complete Response (CR): Disappearance of all target lesions, determined by two separate observations conducted not less than 4 weeks apart. There can be no appearance of new lesions.

Partial Response (PR): At least a 30% decrease in the sum of the longest diameter (LD) of target lesions, taking as reference the baseline sum LD. There can be no appearance of new lesions.

Progressive Disease (PD): At least a 20% increase in the sum of the LD of target lesions (with a minimum absolute increase of 5 mm), taking as reference the smallest sum LD recorded since the treatment started, or the appearance of one or more new lesions.

Stable Disease (SD): Neither sufficient shrinkage to qualify for PR (taking as reference the baseline sum LD) nor sufficient increase to qualify for PD (taking as reference the smallest sum LD since the treatment started).

After the first PD assessment per RECISTv1.1 (=irSD per irRECIST), patients will be evaluated for irPD at least 4 weeks apart according to the following definition:

Immune-related Progressive Disease (irPD): At least a 20% increase in the sum of the LD of target lesions (with a minimum absolute increase of 5 mm), taking as reference the smallest sum LD recorded since the treatment started, or appearance of new lesions since the last evaluation.

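### Section 3.1.4 requires an untreated measurable site at entry, but 7.1.2 carries that protection into target-lesion selection only for irradiated areas, so embolised or ablated targets can dilute growth of untreated tumour

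*Combined protocol and SAP*

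**What the plan says.** **Entry.** Section 3.1.4, like item 4 of the synopsis eligibility list, requires RECIST-measurable disease "in at least one site not previously treated with radiation or liver directed therapy (including bland, chemo- or radio-embolization, or ablation", unless the patient had a complete response to first-line platinum therapy. Section 3.1.3 allows earlier local treatment: "Prior surgical resection, radiation, chemoembolization, radioembolization or other local ablative therapies are permitted if completed ≥ 4 weeks prior to enrollment", with recovery to grade 1 or better.

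**Target lesions.** The note in 7.1.2 restricts one kind of treated lesion. Those "situated in a previously irradiated area will only be considered measurable, if they have had subsequent progression by at least 5 mm". Embolised and ablated lesions appear neither in that note nor in the list of non-measurable disease. The same section says: "All measurable lesions up to a maximum of 2 lesions per organ and 5 lesions in total should be identified as target lesions". On the choice among them it says: "Target lesions should be selected on the basis of their size (non-nodal lesions with the longest diameter". It adds that targets should represent all involved organs and be reproducibly measurable.

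**Progression.** Section 7.1.4.1 defines PD as "At least a 20% increase in the sum of the LD of target lesions (with a minimum absolute increase of 5 mm", measured from the smallest sum on study, or any new lesion. Under Table 5, unequivocal growth of non-target lesions counts only exceptionally. The primary endpoint (2.4.1) is the proportion alive without radiological or clinical progression leading to withdrawal, at 4 months.

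**The concern.** Section 3.1.4 does not accept a locally treated site as proof of measurable disease. Once the patient is enrolled, that caution survives only for irradiated areas. A patient can qualify on a small untreated lesion and then have a larger embolised or ablated lesion put into the target sum because of its size. The cap of two per organ adds to this. Two larger treated liver lesions could take both liver places and leave the qualifying untreated liver lesion as non-target, where growth counts as PD only exceptionally.

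The target sum decides most radiological PD, and so the primary endpoint, as well as PR for ORR. A treated lesion that no longer changes adds a constant to the denominator of the percentage change. There is no control arm in which the same measurement error would occur.

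**Working it through.** **The plan's own figure.** Section 11.2 gives n = 32, 63% against 85%, 1-sided 5% and 80% power. With an exact binomial test, P(X ≥ 25 | 0.63) = 0.0523, just above 5%, and P(X ≥ 26 | 0.63) = 0.0215. The cut-off is therefore 26 of 32, and power is P(X ≥ 26 | 0.85) = 0.805. The stated 80% is reproduced. The protocol does not state a cut-off; 26 is derived here.

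**Dilution of progression.** Let *a* be the total diameter of stable treated targets and *u* that of untreated targets. The untreated tumour must grow by max(0.20 × (a + u), 5 mm) to reach PD. The documents give no diameters, so those below are assumptions.

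| a (mm) | u (mm) | Sum (mm) | Growth needed (mm) | Untreated size at PD (mm) | Growth of untreated |
|---|---|---|---|---|---|
| 0 | 20 | 20 | 5 (floor) | 25 | 25% |
| 20 | 20 | 40 | 8 | 28 | 40% |
| 40 | 20 | 60 | 12 | 32 | 60% |
| 50 | 20 | 70 | 14 | 34 | 70% |
| 60 | 20 | 80 | 16 | 36 | 80% |
| 0 | 30 | 30 | 6 | 36 | 20% |
| 60 | 30 | 90 | 18 | 48 | 60% |

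In the 50 + 20 mm case, growth of the untreated lesion from 20 to 30 mm gives (80 − 70)/70 = 14.3%, which is stable disease. Measured alone, the same lesion has grown 50% and is PD.

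**Response, same 50 + 20 mm case.** A PR needs a fall of 0.30 × 70 = 21 mm.
- Treated lesion inert: complete disappearance of the untreated lesion takes the sum from 70 to 50 mm, a fall of 20/70 = 28.6%. This is stable disease, so a real response is hidden.
- Treated lesion still shrinking after baseline, by an assumed 45%, with untreated tumour unchanged: the sum is 50 × 0.55 + 20 = 47.5 mm, a fall of 22.5/70 = 32.1%. If confirmed, this is a PR created by the earlier procedure.

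**What missed progressions would do to the test.** One patient moves the endpoint by 1/32 = 3.1 points. If a share *q* of true 4-month progressors under the null is called progression-free, the observed rate is 0.63 + 0.37q. The values of *q* are assumed and apply to all progressors, of whom 0.37 × 32 = 11.8 are expected.

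| q | Patients missed (11.8 × q) | Observed rate | P(X ≥ 26) |
|---|---|---|---|
| 0 | 0 | 0.630 | 2.2% |
| 5% | 0.6 | 0.6485 | 3.5% |
| 10% | 1.2 | 0.667 | 5.5% |
| 20% | 2.4 | 0.704 | 12.3% |

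This shows the sensitivity of the test. It does not estimate the bias, because nothing in the documents allows *q* to be set.

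**The case against.** **The selection rule leaves discretion.** A measurable lesion must be accurately measurable, cystic lesions are excluded, and targets should be reproducible and representative. Footnote 6 of the study calendar gives the reading to a radiologist or imaging core. A reader may well pass over an ablation cavity. This stands: the text permits a treated target but does not force one. It also does not tell that reader how to handle embolised or ablated lesions.

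**Other routes to PD remain.** New lesions are PD whatever the sum, and clinical progression counts for the primary endpoint. This stands, and limits the problem to growth confined to existing lesions in patients without clinical progression.

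**Any stable untreated lesion dilutes the sum too.** True, but that is response assessment of tumour the regimen is meant to act on. A treated lesion may be stable because of the earlier procedure.

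**The shrinking-lesion case is narrow.** Entry needs 16 to 24 weeks of platinum, with the last infusion within 4 weeks of consent. The baseline scan is at most 4 weeks before treatment. A further 45% fall after baseline is an assumption, and the case shows only what is possible.

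**Unseen sources.** Section 3.1.4 refers to RECIST v1.1 for measurability, and the 63% benchmark comes from an earlier trial. The documents do not show how either treats such lesions, so a bias in measured PFS may not carry over in full to the comparison with 63%.

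**Stronger readings that the text does not support.** A reader might infer that 3.1.4 bars treated lesions from being measurable, so that 7.1.2 contradicts it. It does not: it asks for at least one untreated site and says nothing against treated lesions as additional measurable disease. A reader might also infer that every error favours the regimen. The 70 to 50 mm example shows otherwise for ORR.

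**Conclusion.** The gap is real. Section 7.1.2 protects target selection from irradiated lesions only. It admits bland- or chemo-embolised and ablated lesions by silence together with its instruction to take all measurable lesions. Whether a radioembolised lesion lies in an irradiated area is unclear. Nothing requires the untreated qualifying lesion to be a target.

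For 4-month PFS the bias is upward where it operates. A stable treated target raises the growth needed for PD, from 25% to 70% with assumed diameters of 50 and 20 mm, and from 25% to between 40% and 80% as the treated diameter runs from 20 to 60 mm. For ORR the net direction is not established. The share of patients with earlier local treatment, and their lesion sizes, are not given, so the total effect on either endpoint cannot be sized. The power calculation is unaffected. This is a cheap improvement worth making, not evidence that the primary analysis is invalid.

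**What to change.** Extend the note in 7.1.2 to the therapies named in 3.1.4. A lesion previously treated with radiation, bland, chemo- or radio-embolisation, or ablation may be a target only if it has progressed by at least 5 mm since that treatment; otherwise it is recorded as non-target. Naming radioembolisation settles the unclear case. Add that at least one untreated lesion qualifying under 3.1.4 must be among the targets, except in patients who enter in complete response.

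This takes two sentences in 7.1.2 and a field for earlier local treatment on the baseline lesion form. The 5 mm criterion is already the protocol's own. No study scans, readers or patients are added, and n = 32 and the 80.5% exact power are unchanged.

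There are two costs. Previously treated patients will have fewer target lesions. Later regrowth in a treated lesion kept as non-target would have to meet the stricter test of unequivocal progression, which Table 5 accepts only exceptionally, so PD in that lesion could be recorded later.

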#### 4.0 SUBJECT SCREENING AND REGISTRATION PROCEDURES

Patient registration for this trial will be centrally managed by the Oncology Clinical Trials Support Unit (i.e. the Coordinating Center) of the University of Michigan Rogel Cancer Center as described below:

A potential study subject who has been screened for the trial and who has signed the Informed Consent document will be initially documented by the participating site on a Screening and Enrollment Log.

It is the responsibility of the local site investigator to determine patient eligibility prior to submitting patient registration request to the Coordinating Center. After patient eligibility has been determined, a copy of the completed Eligibility Worksheet together with all the pertinent deidentified source documents will be submitted by the requesting site to the Coordinating Center, by email to [contact].

A Multi-Site Coordinator of the Coordinating Center, who acts as the registrar, will review the submitted documents and process the registration. Sites should inform the Multi-Site Coordinator of a potential registration by 5 p.m. on the day prior to registration. Same day registrations cannot be guaranteed.

The registrar will send an email to the requesting site registrar to confirm patient registration and to provide the study identification number assigned to the patient. In addition, a copy of the completed Eligibility Worksheet signed and dated by the registrar will be sent back to the requesting site registrar.

Patients found to be ineligible for participation after being consented will be considered screen failures, and documented as such in the Screening and Enrollment Log. These patients will not have study identification number assigned to them, and will not receive study treatment.

#### 5.0 TREATMENT PLAN

# 5.1 Treatment Dosage and Administration

Protocol treatment must start within 14 calendar days of enrollment to the study otherwise the patient will be taken off study. Re-screening is allowed.

Patients will receive combination therapy with PARP inhibitor Rucaparib and anti-PD1 antibody Nivolumab. The safety profile of both agents has been previously evaluated individually.

| Table 1. Treatment Plan |           |               |  |  |  |  |
|-------------------------|-----------|---------------|--|--|--|--|
| Days Treatment Dose     |           |               |  |  |  |  |
| Day 1 every 2 weeks     | Nivolumab | 240 mg IV     |  |  |  |  |
| Days 1-28 every 28 days | Rucaparib | 600 mg PO BID |  |  |  |  |

Rucaparib may be taken with or without food. Patients should take rucaparib doses as close as possible to 12 hours apart, preferably at the same times every day. If a patient misses a dose (i.e., does not take it within 4 hours of the scheduled time), the patient should skip the missed dose and resume taking rucaparib with the next scheduled dose Missed or vomited doses should not be made up. Patients may continue treatment for 2 years in absence of disease progression or unacceptable toxicity.

# 5.2 Toxicities and Dosing Delays/Dose Modifications

Any patient who receives treatment on this protocol will be evaluable for toxicity. Each patient will be assessed for the development of toxicity according to the Time and Events Table (Section 6.2). Toxicity will be assessed according to the NCI Common Terminology Criteria for Adverse Events (CTCAE), version 5.0. Dose adjustments should be made according to the system showing the greatest degree of toxicity.

| Table 2. Dose Modifications |               |                        |               |  |  |  |  |
|-----------------------------|---------------|------------------------|---------------|--|--|--|--|
| Drug                        | Current Dose  | Percentage
Decrease | Modified Dose |  |  |  |  |
|                             | 600 mg PO BID | ~20%                   | 500 mg PO BID |  |  |  |  |
| Pucaparib                   | 500 mg PO BID | 20%                    | 400 mg PO BID |  |  |  |  |
| Rucaparib                   | 400 mg PO BID | ~20%                   | 300 mg PO BID |  |  |  |  |
|                             | 300 mg PO BID | 100%                   | Discontinue   |  |  |  |  |
| Nivolumab                   | 240 mg IV     | 100%                   | Discontinue   |  |  |  |  |

- If more than one toxicity occurs requiring dose reduction, the dose administered should be based on the most severe toxicity.
- Treatment delay of more than 21 days from last intended therapy will result in discontinuation from trial, unless otherwise agreed and documented between the investigator and the sponsor.
- If one of the drugs is held or discontinued due to toxicity attributed to that agent, the patient will be allowed to continue the rest of the combination therapy.
- Nivolumab cannot be dose reduced and can only be discontinued as per detailed algorithms for immune-therapy toxicity management in Appendix III.

# **Rucaparib Dose Modification Criteria**

Treatment with rucaparib should be held if any of the following are observed and a dose reduction should be considered or implemented.

- Grade 3 or 4 hematologic toxicity. Anemia should be managed as described below
- Grade 3 or 4 non-hematologic toxicity (except for alopecia, nausea, vomiting, or diarrhea adequately controlled with systemic antiemetic/antidiarrheal medication administered in standard doses according to the study center routines). Grade 3 or Grade 4 ALT/AST elevations should be managed as described below
- In addition, and at the discretion of the investigator, the dose of rucaparib may be held and/or reduced for unremitting Grade 2 toxicity not adequately controlled by concomitant medications and/or supportive care.
- For patients who meet treatment interruption guidelines above, treatment with rucaparib should be held until the toxicity improves to ≤ CTCAE Grade 2. Twice daily dosing may then be **resumed at either the same dose or a lower dose, per investigator discretion**. If treatment is resumed at the same dose, and the patient experiences the same toxicity, treatment should be interrupted, then resumed at a reduced dose following resolution of the event to ≤ CTCAE Grade 2. If the patient continues to experience toxicity, additional dose reduction steps are permitted; however, the investigator should consult with the sponsor's medical monitor before reducing to 300 mg BID. If a patient continues to experience toxicity despite dose reduction steps to 300 mg BID, or if dosing with rucaparib is interrupted for > 21 consecutive days due to toxicity, treatment should be discontinued, unless otherwise agreed and documented between the investigator and the sponsor.

